9.5 Pharmacokinetic/Pharmacodynamic Assessment

The relationship between the lasmiditan concentrations at 8, 12 and 24 hours (Lasmiditan 100 and 200 mg) and the 8, 12 and 24 hour assessments for SDLP, Lane Exceedance, Speed Deviation, CogScreen SDC number correct, and KSS will be assessed by correlation at each

timepoint separately. Both the Spearman and Pearson correlations will be reported. Tables will provide the correlation coefficient and p-value, which will be provided separately for each treatment group.

For each endpoint of interest, scatterplots including data for both 100 mg and 200 mg will be provided with separate symbols for each dose level.

9.6 Safety and Tolerability Assessments

9.6.1 Adverse Events

Where changes in severity are recorded in the Case Report Form (CRF), each separate severity of the AE will be reported in the listings, only the most severe will be used in the summary tables. A pre-existing condition is defined as an AE that starts before the subject has provided written informed consent and is ongoing at consent. A non-treatment emergent AE is defined as an AE which starts after informed consent but prior to dosing. A treatment-emergent AE is defined as an AE which occurs postdose or which is present prior to dosing and becomes more severe postdose.

All AEs will be listed. Treatment-emergent AEs will be summarized by treatment, severity and relationship to the study drug. The frequency (the number of AEs, the number of subjects experiencing an AE and the percentage of subjects experiencing an AE) of treatment-emergent AEs will be summarized by treatment, Medical Dictionary for Regulatory Activities (MedDRA) version 20.1 system organ class and preferred term. The summary and frequency AE tables will be presented for all causalities and those considered related to the study drug. Any serious AEs will be tabulated.

9.6.2 Concomitant Medication

Concomitant medication will be coded using the WHO drug dictionary (Version September 2017). Concomitant medication will be listed.

9.6.3 Clinical Laboratory Parameters

All clinical chemistry and hematology data will be summarized by parameter and treatment, and listed. Urinalysis data will be listed. Additionally clinical chemistry, hematology and urinalysis data outside the reference ranges will be listed.

Values for any clinical chemistry, hematology and urinalysis values outside the reference ranges will be flagged on the individual subject data listings.

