Period 1, Day 1 subjects will be administered Dose 1 between approximately 0700 hours (7:00 AM) and 1000 hours (10:00 AM). On subsequent dosing days of Periods 2 to 4, doses will be administered at approximately the same time of day as doses in Period 1.

Approximately 8 hours following Dose 1, subjects will perform the CogScreen SDC test, KSS, and indicate their self-perceived safety to drive. Subjects will then perform the Country Vigilance-Divided Attention driving scenario on the CRCDS-MiniSim. Upon completion of the driving scenario, subjects will be administered a VAS to assess subjects' motivation and self-appraisal of their driving performance. Subjects repeat this testing procedure at approximately 12 hours and 24 hours after Dose 1 in all dosing periods.

While resident at the CRU, lights out will occur at approximately 2300 hours (11:00 PM) every night.

Subjects will remain a resident of the CRU from admission until discharge following the completion of study assessments. Blood draws for PK will be taken at pre- and post-dose according to the schedule of activities in all periods.

The total duration of subject participation will be approximately 5 weeks (range 3 to 7 weeks).

Number of Subjects:

Approximately 72 subjects will be enrolled so that 60 healthy volunteers complete the study. This will lead to 90% or more power for testing each of the hypotheses of primary interest regarding the driving assessment endpoints.

Statistical Analysis:**Safety:**

Safety analysis will be based on all subjects enrolled who receive at least 1 dose of study medication. The safety analysis will evaluate AEs and additional safety parameters. The number and percentage of subjects experiencing at least 1 AE will be summarized by body system, preferred term, and treatment. If appropriate, AEs will also be summarized by intensity and relationship to study drug. Serious adverse events, if any, will be tabulated.

Additional safety parameters will be assessed from summaries of physical examinations, 12-lead electrocardiograms and vital signs. Hematology, chemistry, and urinalysis laboratory test results will be categorized relative to the normal ranges. The changes from baseline for each of these parameters at postdose time points will be presented. Complete listings and summary tables for all safety information including AEs, laboratory safety data, vital signs, and physical examination will be included in the study report.

Pharmacokinetics:

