Pharmacokinetic parameter estimates for lasmiditan and its metabolites will be calculated using standard noncompartmental methods of analysis and summarized using descriptive statistics. Plasma concentrations of diphenhydramine will be listed and summarized using descriptive statistics.

Pharmacodynamics:

The primary endpoint, SDLP, will be analyzed using a mixed model with fixed effects for sequence, period, and treatment, and a random effect for subject within sequence for each of the driving time points. Secondary endpoints will be evaluated similarly; however, Lane Exceedance will be log transformed (more specifically $\ln[x+1]$) prior to analyses. Pairwise comparisons for readiness to drive will be analyzed using McNemar test.

Graphical analyses will be performed to explore the relationship between PK concentrations with SDLP and/or other pharmacodynamic (PD) measures. Additional analyses may be performed to further characterize the PK/PD relationship(s), if warranted.

2. Schedule of Activities

Screening		Study Informed Consent
		Medical History
		Subject Eligibility
		Weight/Height (BMI)
		Drug and Alcohol Screen (repeat alcohol screen prior to Driving Sim Training/Practice if performed at a separate visit)
		Vital Signs
		Physical Examination (may be performed through Day -1)
		Epworth Sleepiness Scale
		Clinical Laboratory Tests
		Twelve-Lead ECG
		Temperature
		Serum Pregnancy Test (females only)
		CogScreen SDC Training/Screening
		Driving Sim Training/Screening
		Simulator Sickness Questionnaire
		Concomitant Medication assessment
Day -1 (Period 1)	Admission to Clinic	
		Confirm Subject Eligibility
		Drug and Alcohol Screen
		Serum Pregnancy Test (females only)
		Vital Signs
		Directed Physical Examination (symptom driven)
		CogScreen SDC Practice
		Driving Sim Practice
		Adverse Event Assessment
		Concomitant Medication Assessment (monitor throughout study)
Day 1 (Periods 1-4)	Predose	
		Vital Signs
		Directed Physical Examination (symptom driven)
		Lasmiditan and Metabolites PK Sampling (predose)
		Diphenhydramine PK Sampling (predose)
	+0.0 h	Study Drug Administration (Dose 1)
	+0.5 h	Lasmiditan and Metabolites PK Sample ^a
	+1.0 h	
		Lasmiditan and Metabolites PK Sample ^a
		Breakfast
	+1.5 h	Lasmiditan and Metabolites PK Sample ^a
	+2.0 h	Vital Signs/Lasmiditan and Metabolites PK Sample ^a
	+3.0 h	Lasmiditan and Metabolites PK Sample ^a
	+4.0 h	
		Vital Signs/Lasmiditan and Metabolites PK Sample ^a
		Lunch
	+6.0 h	

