		Lasmiditan and Metabolites PK Sample ^a
		Study Drug Administration (Dose 2)
+8.0 h		
		KSS ^b
		Adverse Event Assessment ^b
		CogScreen SDC Test ^b
		Self-Perceived Questionnaire (safe to drive)
		Lasmiditan and Metabolites PK Sample ^a
		Diphenhydramine PK Sample ^a
		CVDA Drive
		VAS (immediately after drive)
+10.0 h		
		Lasmiditan and Metabolites PK Sample ^a
		Study Drug Administration (Dose 3)
+11.0 h		Dinner
+12.0 h		
		KSS ^b
		Adverse Event Assessment ^b
		CogScreen SDC Test ^b
		Self-Perceived Questionnaire (safe to drive)
		Lasmiditan and Metabolites PK Sample ^a
		Diphenhydramine PK Sample ^a
		CVDA Drive
		VAS (immediately after drive)
Day 2 (Periods 1-4)	+22 h	Study Drug Administration (Dose 4)
	+23 h	Breakfast
	+24 h	
		KSS ^b
		Adverse Event Assessment ^b
		CogScreen SDC Test ^b
		Self-Perceived Questionnaire (safe to drive)
		Lasmiditan and Metabolites PK Sample ^a
		Diphenhydramine PK Sample ^a
		CVDA Drive
		VAS (immediately after drive)
	+36 h	Lasmiditan and Metabolites PK Sample ^a
Day 3 (Periods 1-4)	+48 h	Lasmiditan and Metabolites PK Sample ^a
Discharge (Day 3, Period 4)	Discharge from Clinical Unit	
		Vital Signs
		Physical Examination
		Clinical Laboratory Tests
		Adverse Event Assessment
		Concomitant Medication Assessment
Early Discontinuation		
		Vital Signs

		Physical Examination
		Clinical Laboratory Tests
		Twelve-Lead ECG
		Urinalysis Samples
		Serum Pregnancy Test (females only)
		Adverse Event Assessment
		Concomitant Medication assessment
Within 5 to 9 days after Discharge	Follow-up	
		Vital Signs
		Physical Examination
		Clinical Laboratory Tests
		Twelve-Lead ECG
		Urinalysis Samples
		Serum Pregnancy Test (females only)
		Adverse Event Assessment
		Concomitant Medication Assessment

Abbreviations: BMI = body mass index; CVDA = Country Vigilance-Divided Attention; ECG = electrocardiogram; h = hours, KSS = Karolinska Sleepiness Scale; PK = pharmacokinetic; SDC = Symbol Digit Coding; VAS = Visual Analog Scale.

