9.4. Safety

9.4.1. Laboratory Tests

For each subject, laboratory tests detailed in [Appendix 2](#) should be conducted according to the Schedule of Activities (Section 2).

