Appendix 5. Blood Sampling Summary

This table summarizes the approximate number of venipunctures and blood volumes for all blood sampling (screening, safety laboratories, and bioanalytical assays) during the study.

Protocol H8H-MC-LAIF Sampling Summary

Purpose	Blood Volume per Sample (mL)	Number of Blood Samples	Total Volume (mL)
Screening tests ^a	19.5	1	19.5
Clinical laboratory tests ^a	12.5	2	25
Lasmiditan and metabolite pharmacokinetics	2	52	104
Diphenhydramine pharmacokinetics	2	16	32
Total			180.5
Total for clinical purposes (rounded up to the nearest 10 mL)			190

**Appendix 6. Protocol Amendment H8H-MC-LAIF(a)
Summary: A Phase I, Randomized, Subject- and
Investigator-Blind, Placebo-Controlled, 4-Period Cross-
Over Study Assessing the Duration of Effect of
Lasmiditan on Simulated Driving Performance in
Healthy Volunteers**

Overview

Protocol H8H-MC-LAIF A Phase I, Randomized, Subject- and Investigator-Blind, Placebo-Controlled, 4-Period Cross-Over Study Assessing the Duration of Effect of Lasmiditan on Simulated Driving Performance in Healthy Volunteers has been amended. The new protocol is indicated by Amendment (a) and will be used to conduct the study in place of any preceding version of the protocol.

The overall change and rationale for the change made to this protocol are as follows:

- Pharmacogenetic blood sampling was removed from study in agreement with the Sponsor's Tailored Therapeutics group. The number of healthy volunteers is relatively small (<100) and a pharmacogenetic sample collection is unlikely to enable investigation of pharmacogenetic characteristics in migraine response to lasmiditan.

Revised Protocol Sections

Note: All deletions have been identified by ~~strike-throughs~~.
All additions have been identified by the use of underline.

2. Schedule of Activities

Screening		Study Informed Consent
		Medical History
		Subject Eligibility
		Weight/Height (BMI)
		Drug and Alcohol Screen (repeat alcohol screen prior to Driving Sim Training/Practice if performed at a separate visit)
		Vital Signs
		Physical Examination (may be performed through Day -1)
		Epworth Sleepiness Scale
		Clinical Laboratory Tests
		Twelve-Lead ECG
		Temperature
		Serum Pregnancy Test (females only)
		CogScreen SDC Training/Screening
		Driving Sim Training/Screening
		Simulator Sickness Questionnaire
		Concomitant Medication assessment
Day -1 (Period 1)	Admission to Clinic	
		Sample for Pharmacogenetic Analysis (prior to or on Day 1, Period 1)

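### Laboratory data are to be summarised by treatment, but a completer's scheduled post-dose draws all come after all four treatments

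*SAP*

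**What the plan says.** SAP Section 9.6.3 gives the layout: "All clinical chemistry and hematology data will be summarized by parameter and treatment, and listed". It adds listings of urinalysis and of out-of-range values. It names no laboratory baseline and does not say how a value is assigned to a treatment.

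Protocol Section 9.4.1 ties the timing of the tests to the schedule: they "should be conducted according to the Schedule of Activities (Section 2". In that schedule, "Clinical Laboratory Tests" appears in four places:

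- in the screening block;
- in the block headed "Discharge (Day 3, Period 4";
- in the follow-up block, timed "Within 5 to 9 days after Discharge";
- in the block headed "Early Discontinuation", for subjects who stop.

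No safety laboratory test is scheduled on Day -1, at predose, or at any other point within or between the periods.

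For laboratory and other safety data, the protocol synopsis promises more than SAP 9.6.3 delivers: "The changes from baseline for each of these parameters at postdose time points will be presented". It also says that laboratory results will be categorised against normal ranges. Protocol Section 10.3.1.2 asks for listings and standard descriptive statistics and does not call for a split by treatment.

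**The concern.** In a crossover, a by-treatment safety table is informative when each treatment period has its own measurement. The vital signs plan meets that condition. The schedule has measurements at predose and at 2 and 4 hours in every period, and SAP Section 9.6.4 takes the predose value of each period as baseline. The laboratory data have no such structure.

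A table with columns for placebo, two lasmiditan doses and diphenhydramine invites the reader to compare across columns. If the subjects behind each column have had all four treatments, a drug-related change in an analyte, such as a liver enzyme, could raise the placebo column as readily as a lasmiditan column. Similar columns could then be read as evidence of no effect.

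**Working it through.** **Count of draws.** Appendix 5 of the protocol gives one screening sample of 19.5 mL, two samples of 12.5 mL in the row "Clinical laboratory tests", 52 lasmiditan samples of 2 mL and 16 diphenhydramine samples of 2 mL. The stated total reproduces:

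1 × 19.5 + 2 × 12.5 + 52 × 2 + 16 × 2 = 19.5 + 25 + 104 + 32 = 180.5 mL.

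The total checks only the table's arithmetic. What matters here is the two laboratory samples after screening, which match the discharge and follow-up draws in the schedule. A completer therefore has no scheduled laboratory value between screening and Day 3 of Period 4.

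**Who falls in each column.** The SAP gives no attribution rule, so I assume the last treatment received. Reading the sequence table in SAP Section 5 for completers:

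| Column (Period 4 treatment) | Sequence | Already received in Periods 1 to 3 |
|---|---|---|
| Lasmiditan 200 mg | 1 | Placebo, lasmiditan 100 mg, diphenhydramine |
| Diphenhydramine | 2 | Lasmiditan 100 mg, lasmiditan 200 mg, placebo |
| Placebo | 3 | Lasmiditan 200 mg, diphenhydramine, lasmiditan 100 mg |
| Lasmiditan 100 mg | 4 | Diphenhydramine, placebo, lasmiditan 200 mg |

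With equal allocation and 60 completers, each column holds 60/4 = 15 subjects, all from one sequence. (The enrolled figure, 72/4 = 18, includes subjects who do not finish.) Among completers, treatment is fully confounded with sequence, and cumulative exposure is the same four treatments in every column. Screening values precede all dosing and belong to no column.

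**Timing in the placebo column.** The anticipated period starts are Days 1, 4, 7 and 10 (protocol Section 5.4), so Day 3 of Period 4 is Day 12. For sequence 3, the time from the start of each earlier period to the discharge draw is:

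- lasmiditan 200 mg: 12 − 1 = 11 days;
- diphenhydramine: 12 − 4 = 8 days;
- lasmiditan 100 mg: 12 − 7 = 5 days.

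Each of the three gaps between periods can be lengthened by at most 2 days, so the first figure can reach 11 + 3 × 2 = 17 days. Follow-up comes 5 to 9 days after discharge.

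**Does washout separate the treatments?** The minimum washout is 3 days. The protocol itself allows for laboratory abnormalities that last longer: Section 8.1 refers to transaminase elevations that persist for more than 2 weeks, and Section 9.4.4.1 repeats abnormal liver tests after 3 to 5 days. Clearance of the drug does not ensure that an analyte has returned to its starting value.

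**Subjects who stop early.** The plan allows for about 72 − 60 = 12 non-completers. A subject who stops in Period 1 has had one treatment; one who stops in Period 2 or 3 has had at most two or three. Under last-treatment attribution, a sequence 3 subject who stops in Period 1 falls in the lasmiditan 200 mg column, so the match between column and sequence is exact for completers only.

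**What pooling gains.** A by-visit summary uses all 60 completers instead of 15. With a common SD, the standard error of a mean change is multiplied by √(15/60) = 0.5.

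**The case against.** The strongest reply is that little depends on this table. SAP Section 9.6.9 plans no inferential safety analysis. SAP 9.6.3 requires full listings, flags for out-of-range values and a separate out-of-range listing. Liver elevations trigger repeat tests, and hepatic data are listed separately (SAP 9.6.6). An individual abnormality would be visible whatever the columns are called. This stands, and it limits the point to how the summary is presented. It also means that the halved standard error has little practical weight, because no laboratory comparison or interval is planned. It does not justify a by-treatment heading that the draws cannot support.

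A second reply is that last-treatment attribution is inferred. The SAP leaves table layout to a separate shell document, which is not available here and might define something else. This also stands. But no attribution rule can recover a single-treatment value for completers, because no scheduled draw follows only one, two or three of their treatments.

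A reader might go further and infer that every subject in every column has had all four treatments. The documents do not support that, because the early-discontinuation draws can follow fewer. Repeat liver tests could also fall within a period, but they are triggered by an abnormality and cannot support a routine by-treatment summary.

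**Conclusion.** The point holds for subjects who complete. Their two scheduled post-dose draws both follow all four treatments, so the planned by-treatment summary cannot separate the treatments and would mislead if read as a comparison. The SAP also leaves the attribution rule and the laboratory baseline unstated, and Section 9.6.3 plans no summary of change, although the protocol synopsis promises one. SAP Section 11 does not record that difference.

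The description of each column as one sequence of about 15 rests on last-treatment attribution, equal allocation and 60 completers. The interval of about 11 days rests on the anticipated schedule.

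The effect is confined to descriptive safety tables; the primary SDLP analysis is untouched. It would be too strong to infer that a laboratory signal would be hidden, since the listings show each subject's values.

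**What to change.** In SAP Section 9.6.3:

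- Replace the by-treatment layout with a summary by parameter and visit (screening, discharge, follow-up), pooled over sequences, with change and shift from screening. This makes screening the stated laboratory baseline and delivers the change from baseline promised in the synopsis.
- Show early-discontinuation draws as a separate row, and list them with the treatments received to date.
- List all values with sequence and last treatment received.
- State that laboratory changes in completers cannot be attributed to a single treatment.

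The cost is a small change to SAP wording and one table shell, with no new data. The by-treatment layout is lost.

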9.6.4 Vital Signs

Where two or more repeat measurements are performed for vital signs, the median of the original and the repeat values will be used in all subsequent calculations. Where only one repeat measurement is performed for vital signs, the repeat value will be used in all subsequent calculations.

Vital signs data will be summarized by treatment together with changes from baseline, where baseline is defined as predose of each period.

Furthermore, values for individual subjects will be listed.

9.6.5 Electrocardiogram (ECG)

For each subject, ECGs will be performed for safety purposes only, and will not be reported.

9.6.6 Hepatic Monitoring

If a subject experiences elevated alanine aminotransferase (ALT) $\geq 3 \times$ upper limit of normal (ULN), alkaline phosphatase (ALP) $\geq 2 \times$ ULN, or elevated total bilirubin (TBL) $\geq 2 \times$ ULN, liver tests will be performed to confirm the abnormality.

The subjects' liver disease history and associated person liver disease history data will be listed. Any concomitant medication of acetaminophen/paracetamol will be listed. Results from any hepatic monitoring procedures, such as a magnetic resonance elastography (MRE) scan, and a biopsy assessment will be listed, if performed.

Hepatic risk factor assessment data will be listed. Liver related signs and symptoms data will be summarized by treatment and listed. Alcohol and recreational drug use data will also be listed.

All hepatic chemistry, hematology, coagulation, and serology data will be listed. Values outside the reference ranges will be flagged on the individual subject data listings.

9.6.7 Meals

Meal data will be listed for individual subjects.

9.6.8 Other assessments

All other safety assessments not detailed in this section will be listed but not summarized or statistically analyzed.

9.6.9 Safety and Tolerability Statistical Methodology

No inferential statistical analyses are planned.

10. INTERIM ANALYSES

No interim statistical analyses are planned.

11. CHANGES FROM THE PROTOCOL SPECIFIED STATISTICAL ANALYSES

The mixed model specification was updated to use a REPEATED statement rather than a RANDOM statement in the SAS[®] MIXED procedure, to more readily allow for the estimation of an unstructured covariance matrix. Additional details regarding model specification and outputs are also provided in Section 9.4.2.

13. DATA PRESENTATION

13.1 Derived Parameters

Individual derived parameters (e.g. PK parameters) and appropriate summary statistics will be reported to three significant figures. Observed concentration data, e.g. C_{\max} , should be reported as received. Observed time data, e.g. t_{\max} , should be reported as received. N and percentage values should be reported as whole numbers. Median values should be treated as an observed parameter and reported to the same number of decimal places as minimum and maximum values.

13.2 Missing Data

Missing data will not be displayed in listings.

13.3 Insufficient Data for Presentation

Some of the TFLs may not have sufficient numbers of subjects or data for presentation. If this occurs, the blank TFL shell will be presented with a message printed in the centre of the table, such as, "No serious adverse events occurred for this study."
